9.5. Concomitant Medications

Concomitant medications administered for the treatment of existing or new comorbidities, not otherwise prohibited by the protocol, will be recorded in the subject's source document(s) and the CRF.

9.5.1. Prohibited Medications

Subjects must not receive any treatments in the study eye for nAMD or any systemic treatments for nAMD not approved in the protocol. The list of prohibited treatments provided below is not intended to be comprehensive, but rather to help guide the Investigator's medical judgment. In cases where a subject presents with a treatment not included on the following list or should there be any question on the part of the Investigator, Investigators are encouraged to confer with the Medical Monitor for any clarification.

Use of the following treatments is prohibited at any time during the study:

In cases where there is anticipated need for any of the treatments listed here during the study (post Visit 5), or if a subject presents to the Investigator having initiated treatment during the study with one of these treatments, it is the responsibility of the Investigator to notify the Sponsor immediately. If additional therapy is necessary to treat worsening of nAMD in the study

eye and normal standard of care requires additional intervention, the treatment(s) should be recorded in the subject's source document(s) and CRF and should follow the guidelines presented for additional therapy criteria. Subjects will not be discontinued from the study because of initiation of or change in a prohibited medication. Any use of a prohibited medication will be documented as a protocol deviation.

9.6. Treatment Compliance

No study medication will be dispensed or administered to subjects during this extension study; therefore, an assessment of subject treatment compliance is not applicable.

Study medication will only be administered by trained study Investigators in the Parent study.

9.7. Randomization and Masking

This is an open-label study; no masking is necessary.

This is non-interventional extension study. Subjects will remain in the dose cohort they participated under during the Parent study.

10. STUDY DRUG MATERIALS AND MANAGEMENT

This is an open-label, non-interventional extension of the Parent study, CLS1002-101. No study drug will be dispensed or administered to the subjects as part of this protocol. Additional treatments administered during this study will be recorded as concomitant and/or rescue medications. Storage of permitted additional treatments should be according to the Prescribing Information for the individual treatment(s) and is the responsibility of the Investigator.

11. ASSESSMENT OF SAFETY

Measurements obtained from the assessments of safety will be recorded in the subject's source document(s) and the CRF.

11.1. Safety Variables

Safety assessments will include [REDACTED]

[REDACTED] In-office urine pregnancy assessment will be performed on females of childbearing potential. All safety assessments will be assessed at visits as specified in the Time and Events Schedule in Section 20.

The determination whether additional treatment is needed will include reference to data collected during the Parent study (Section 9.4.1).

11.1.1. Best Corrected Visual Acuity

Best corrected visual acuity will be evaluated by ETDRS using standardized lighting and standardized lanes. The results shall be reported as the number of letters read correctly. Visual acuity testing should precede any examination requiring contact with the eye.

In order to provide standardization and well-controlled assessments of BCVA during the study, all BCVA assessments must be performed by trained staff who are certified on the study procedure using certified visual acuity (VA) equipment/lanes. BCVA will be performed in the study eye at Visits 6 and 7 (Weeks 16 and 20) and in both eyes at Visit 8 (Week 24).

11.1.2. Spectral Domain Optical Coherence Tomography

Retinal thickness and disease characterization will be assessed via SD-OCT. The SD-OCT instrument and technician must be certified before screening any subjects. The technician is encouraged to use the same certified equipment throughout the subject's study participation. All images should be taken by the same technician, whenever possible, on each subject per research site.

[REDACTED]

11.1.3. Intraocular Pressure

Intraocular pressure will be measured by applanation tonometry and results will be recorded in mmHg. Where available, Goldmann applanation tonometry should be used at all visits.

Tonopens may be used for post-injection pressure checks and in cases where no Goldmann is available. The technician is encouraged to use the same tonometry method throughout the subject's study participation.

If the subject's study eye qualifies for additional therapy at the final visit (Visit 5) of the Parent study and receives additional therapy as a result, following enrollment into this extension study, IOP will be measured in the study eye 10 to 30 minutes after treatment is administered if at Enrollment Day or any time during Enrollment Day if administered prior. IOP will be measured at Visits 6, 7 and 8 (Weeks 16, 20 and 24) in both eyes. If additional therapy is administered

PRN at Visits 6 and/or 7, then IOP will be measured twice: in both eyes before treatment and in the study eye 10 to 30 minutes after treatment is administered. Tonometers must be calibrated for accuracy before the first subject visit at that site and according to the manufacturer specifications during the study, until the last subject has exited the study at that site.

11.1.4. Slit-lamp Biomicroscopy

Slit-lamp biomicroscopy, including magnification, will be performed consistent with standard clinical practice. This procedure should be conducted in the same manner for all subjects and will include an assessment of each of the following as normal or abnormal: eyelids, pupil and conjunctiva, cornea, anterior chamber, iris, and lens. All abnormal findings will be described. Slit lamp biomicroscopy will be assessed at all visits.

If the subject's study eye qualifies for additional therapy at the final visit (Visit 5) of the Parent study and receives additional therapy as a result, following enrollment into this extension study, then slit-lamp biomicroscopy will be performed in the study eye after treatment is administered at Enrollment Day or any time during Enrollment Day if administered prior. Slit-lamp biomicroscopy will be performed in the study eye at Visits 6 and 7 (Weeks 16 and 20) and in both eyes at Visit 8 (Week 24). If additional therapy is administered PRN at Visits 6 and/or 7, then slit-lamp biomicroscopy will be performed twice in the study eye: before treatment and after treatment is administered.

11.1.4.1. Cataract Lens Grading

If an abnormal finding of cataract is noted during the slit-lamp examination, the cataract should be graded for nuclear opalescence, cortical opacity, and posterior subcapsular opacity. Graders must verify training on the grading procedures. Cataract classification will be based on the Lens Opacities Classification System III (LOCS III) grading scale ([Chylack, 1993](#)). Grading should be done by the same Investigator, whenever possible, on each subject per research site.

11.1.4.2. Anterior Chamber Cells

Anterior chamber cells will be assessed clinically using a field size of 1 mm slit beam and using a standardized grading scale ranging from 0 to 4+, as defined in Table 5 ([SUN, 2005](#)).

Table 5: Anterior Chamber Cells Grading Scale

| Score | Cells in Field |
|--------------|-----------------------|
| 0 | <1 |
| 0.5+ | 1-5 |
| 1+ | 6-15 |
| 2+ | 16-25 |
| 3+ | 26-50 |

Table 5: Anterior Chamber Cells Grading Scale (Continued)

| Score | Cells in Field |
|-------|----------------|
| 4+ | >50 |

11.1.4.3. Anterior Chamber Flare

Anterior chamber flare will be assessed clinically via slit lamp using a standardized scale ranging from 0 to 4+, as defined in Table 6 ([SUN, 2005](#)).

Table 6: Anterior Chamber Flare Grading Scale

| Score | Description |
|-------|--|
| 0 | None |
| 1+ | Faint |
| 2+ | Moderate (iris and lens details clear) |
| 3+ | Marked (iris and lens details hazy) |
| 4+ | Intense (fibrin or plastic aqueous) |

11.1.5. Indirect Ophthalmoscopy

Indirect ophthalmoscopy should be performed according to the Investigator's standard procedure. This procedure should be the same for all subjects observed at the Investigator's site. The fundus will be examined thoroughly, and the following variables will be assessed as normal or abnormal (including but not limited to): vitreous, retina, choroid, and optic nerve/disc, appearance of vessels, and absence of neovascularization. Indirect ophthalmoscopy will be assessed at all visits.

If the subject's study eye qualifies for additional therapy at the final visit (Visit 5) of the Parent study and receives additional therapy as a result, following enrollment into this extension study, then indirect ophthalmoscopy will be performed in the study eye after treatment is administered at Enrollment Day or any time during Enrollment Day if administered prior. Indirect ophthalmoscopy will be performed in the study eye at Visits 6 and 7 (Weeks 16 and 20) and in both eyes at Visit 8 (Week 24). If additional therapy is administered PRN at Visits 6 and/or 7, then indirect ophthalmoscopy will be performed twice in the study eye: before treatment and after treatment is administered.

11.1.5.1. Vitreous Haze

Vitreous haze will be assessed clinically via indirect ophthalmoscopy using a standardized photographic scale ranging from 0 to +4, as defined in Table 7 ([Nussenblatt, 1985](#) as modified in [Lowder, 2011](#)).

Table 7: Scale for Determining Degree of Vitreous Haze

| Score | Description |
|-------|-----------------|
| 0 | No inflammation |

Table 7: Scale for Determining Degree of Vitreous Haze (Continued)

| Score | Description |
|-------|--|
| +0.5 | Trace inflammation (slight blurring of the optic disc margins and/or loss of the nerve fiber layer reflex) |
| +1 | Mild blurring of the retinal vessels and optic nerve |
| +1.5 | Optic nerve head and posterior retina view obscuration greater than +1, but less than +2 |
| +2 | Moderate blurring of the optic nerve head |
| +3 | Marked blurring of the optic nerve head |
| +4 | Optic nerve head not visible |

11.1.6. Fluorescein Angiography

11.1.7. Fundus Photography

11.1.8. Vital Signs

11.1.9. Review of Body Systems (Physical Examination)

11.1.9.1. Pregnancy Screen

Urine pregnancy tests will be performed on all females of childbearing potential on Enrollment Day and at Visit 8 (Week 24).

11.2. Adverse and Serious Adverse Events

11.2.1. Definition of Adverse Events

11.2.1.1. Adverse Event (AE)

An AE is the development of an undesirable medical condition or the deterioration of a pre-existing medical condition in a subject participating in a clinical study, whether or not considered to have a causal relationship with the study drug, SCS Microinjector (e.g., endophthalmitis, choroidal hemorrhage, etc.) or study procedure (e.g., AEs related to the volume of the injection such as transient increase in intraocular pressure). In clinical studies, an AE can include an undesirable medical condition occurring at any time, including baseline or washout periods, even if no study treatment has been administered.

All AEs that occur after any subject has signed informed consent, or during the study participation, whether or not they are related to the study drug, SCS Microinjector or study procedure, must be recorded on the appropriate form provided. Each AE is to be evaluated for duration, intensity, and causal relationship with the study medication or other factors.

At every visit, patients should be asked about AEs in an open-ended manner as well as asked about the status of any previously reported AEs.

When possible, a specific disease or syndrome rather than an individual associated sign or symptom should be identified by the Investigator and recorded on the form. If an observed or reported sign or symptom is not considered a component of a specific disease or syndrome by the Investigator, it should be recorded as a separate AE on the form.

NOTE: A significant or unexpected worsening or exacerbation of the condition/indication under investigation should be reported as an AE. However, anticipated day-to-day fluctuations or expected progression of the disease under investigation (based upon the Investigator's clinical judgment) are not to be considered AEs.

11.2.1.2. Abnormal Clinical Assessments as Adverse Events and Serious Adverse Events

Abnormal assessments (e.g., ocular assessments and vital signs) that are judged by the Investigator as clinically significant will be recorded as AEs or SAEs if they meet the definition of an AE or SAE. Abnormal clinical assessments and any clinically significant abnormal laboratory findings that are detected during the study or are present at baseline and significantly worsen following exposure to study drug are to be reported as AEs or SAEs. However, clinically significant abnormal laboratory findings or other abnormal assessments that are associated with the disease being studied, unless judged by the Investigator as more severe than expected for the patient's condition, or that are present at the start of the study and do not worsen, should not be reported as AEs or SAEs.

The Investigator will exercise medical and scientific judgment in deciding whether an abnormal laboratory or assessment is clinically significant and if it requires reporting.

11.2.1.3. Serious Adverse Event (SAE)

An SAE is defined as an AE that meets any of the following criteria:

- Results in death.
- It is immediately life-threatening. NOTE: The term “life threatening” refers to an event in which the patient is at risk of death at the time of the event. It does not refer to an event which hypothetically might have caused death if it was more severe.
- It requires in-patient hospitalization or prolongation of existing hospitalization. NOTE: Hospitalization for an elective or procedure planned prior to the signing of the informed consent to treat a preexisting condition is not considered an SAE unless it results in one of the other outcomes listed in this section.
- It results in persistent or significant disability or incapacity.
- Results in a congenital abnormality or birth defect.
- It is an important medical event that may jeopardize the patient or may require medical intervention to prevent one of the outcomes listed above.

All SAEs that occur after any subject has signed informed consent, whether or not they are related to the study, must be recorded on the forms provided.

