Results from Cohort 1 of the open label, dose-escalation Parent study, CLS1002-101, support the rationale for conducting an extension of follow-up of subjects receiving CLS-AX in cohorts 2, 3 and 4. A total of 6 subjects were enrolled into Cohort 1 of the Parent study. Of these subjects, 2 subjects completed the study without meeting the pre-specified criteria for the administration of additional therapy, demonstrating at least 3 months durability of the effect of CLS-AX on BCVA and central subfield retinal thickness assessed via optical coherence tomography. Without longer follow-up, a more comprehensive assessment of durability will not be possible. Given the anticipated similar or longer durability of effect, a longer duration of follow-up is justified for cohorts 2, 3 and 4, to more fully assess long-term safety, tolerability and effects on visual function and ocular anatomy.

All subjects entering this trial will have received CLS-AX at Visit 2 (Baseline, Day 1) of the Parent study, CLS1002-101, as investigational product. The objective of the Parent study is to evaluate the safety and tolerability, over 12 weeks of follow-up, of a single dose of suprachoroidally administered CLS-AX in subjects with nAMD who show stable visual acuity following 3 or more injections with an intravitreal anti-VEGF therapy in the preceding 5 months.

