7. INVESTIGATIONAL PLAN

7.1. Overall Study Design

This is an open-label, non-interventional extension study of up to 12 weeks in duration in subjects participating in and completing Cohorts 2, 3 and 4 of the Parent study, CLS1002-101.

[REDACTED]

The Parent study design includes 4 dose cohorts of approximately 5 enrolled subjects in each cohort. Subject eligibility will be established at Visit 1, Screening (Day -28 ± 3 days). Eligible subjects will receive an IVT injection of aflibercept, 2 mg (0.05 mL), at Visit 1 (Screening), followed by a suprachoroidal injection of CLS-AX at Visit 2, Baseline (Day 1) upon enrollment.

[REDACTED]

This extension study includes 4 clinic visits (Enrollment Day, and Visits 6, 7 and 8; Weeks 12, 16, 20 and 24) over a maximum of 12 weeks, for a total of up to 24 weeks follow-up from the time of CLS-AX administration at Visit 2 (Baseline, Day 1) in the Parent study.

[REDACTED]

[REDACTED]

To ensure subjects have adequate time to evaluate and provide informed consent to participate in the extension study, consent may be obtained prior to, as part of, or after Visit 5 (no later than within 48 hours) of the Parent study. Eligibility assessments will only be performed after consent has been obtained and after all the Visit 5 assessments of the Parent study have been completed and the subject has exited the Parent study.

[REDACTED]

[REDACTED]

Post additional treatment assessment of the study eye will be conducted.

Ideally, Enrollment Day assessments should occur on the same day as Visit 5 of the Parent study especially for those subjects who met additional therapy criteria at Visit 5 of the Parent study and were administered additional therapy, so that post therapy assessments may be performed as part of this extension study's Enrollment Day. If due to time constraints, it is not possible to conduct post therapy assessments on the same day as the injection of the additional therapy after exiting Visit 5 of the Parent study, the assessments should occur no later than within 48 hours of having received the additional therapy, upon exiting the Parent study at Visit 5.

The 3 dose cohorts from the Parent study that will be enrolled into this extension study include the following doses:

- [REDACTED]
- [REDACTED]
- [REDACTED]

Subjects enrolled into this extension study will participate in three monthly follow-up visits (Visits 6, 7 and 8; Weeks 16, 20 and 24) [REDACTED]

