7.2. Endpoints

In this extension study, Baseline will be defined as the last non-missing value prior to CLS-AX administration at Visit 2 (Day 1) in the Parent study, CLS1002-101.

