7.2.1. Primary Endpoint

The primary endpoint for evaluating the continued tolerability of the three dose cohorts will be based on the number of subjects experiencing treatment-emergent (TEAEs), and serious adverse events (SAEs). Treatment-emergent adverse events are defined as an event that emerges following treatment with CLS-AX (administered at Visit 2 (Baseline, Day 1) of the Parent study, CLS1002-101), having been absent pre-treatment or worsens relative to the pre-treatment state.

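### The planned-hospitalization exception to the SAE definition is tied to extension consent, which follows CLS-AX dosing, so one type of admission for a post-dose condition can lose its serious classification

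*Combined protocol and SAP*

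**What the plan says.** Section 11.2.1.3 makes inpatient hospitalization a seriousness criterion and then adds an exception. Admission for an elective or previously arranged procedure "planned prior to the signing of the informed consent to treat a preexisting condition is not considered an SAE". The exception carries a limit of its own, since it applies only "unless it results in one of the other outcomes listed in this section". The section does not define a preexisting condition.

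On the timing of consent, Section 7.1 states that "consent may be obtained prior to, as part of, or after Visit 5 (no later than within 48 hours) of the Parent study". Sections 8.4.1 and 8.4.2 repeat this, and Section 12.4.1 names the consent as the one for the extension. On the timing of dosing, Section 5 states: "All subjects entering this trial will have received CLS-AX at Visit 2 (Baseline, Day 1) of the Parent study".

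The primary endpoint (Section 7.2.1) counts subjects with TEAEs and with SAEs. A TEAE is "an event that emerges following treatment with CLS-AX" that was absent, or less severe, before treatment. Section 12.5.2 restricts both the AE and the SAE summaries to TEAEs.

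Section 11.2.1.2, on abnormal assessments, uses two reference points in consecutive sentences. Abnormalities that "are present at baseline and significantly worsen following exposure to study drug are to be reported as AEs or SAEs". The next sentence exempts certain disease-related findings, "or that are present at the start of the study and do not worsen, should not be reported as AEs or SAEs". Section 7.2 fixes the first of these reference points: "Baseline will be defined as the last non-missing value prior to CLS-AX administration at Visit 2 (Day 1) in the Parent study".

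**The concern.** An exception for planned admissions normally removes procedures for conditions that predate exposure. That works when consent comes before the first dose. Here the order is reversed: every subject was dosed in the Parent study, and the extension consent comes later. The same wording therefore also reaches conditions that began after CLS-AX was given.

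SAEs are one of the two components of the primary endpoint, and Section 11.2.4 makes serious status the trigger for reporting to the sponsor within 24 hours. An error by this route can only lower the SAE count. No formal testing is planned, so the small per-cohort counts are themselves the primary result.

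**Working it through.** The plan gives no figure to reproduce. The check sets the sections against each other and then gives a scale.

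**Step 1. Reference points.**
- Dosing: Parent Visit 2, Day 1 (Section 5).
- Extension consent: before, at, or up to 48 hours after Parent Visit 5, Week 12 (Sections 7.1, 8.4.1, 8.4.2). No earliest time is set, so Week 12 is typical rather than exact.
- Emergence: judged against the state before CLS-AX (Section 7.2.1).
- Planned-admission exception: judged at consent (Section 11.2.1.3).

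The last two differ by the interval from dosing to extension consent.

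**Step 2. One illustrative subject.** A condition appears at Week 8. An elective admission is arranged before extension consent and takes place at Week 14.
- Under Section 7.2.1 the condition is treatment-emergent, since it was absent before dosing.
- Under Section 11.2.1.3 the admission was planned before consent. If preexisting is read as present before consent, the admission is not an SAE.
- Under Section 11.2.4 an event not classed as serious does not trigger the 24-hour report.

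Section 11.2.2.2 lists a pre-treatment condition among possible causes of an AE, so the protocol has a term tied to treatment. The exception does not use it.

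**Step 3. What pooling preserves.** Sections 12, 12.4.1 and 12.5 bring Parent and extension data together by dose cohort. The Week 8 condition, recorded as a Parent AE, stays in the TEAE tables. If the Parent study classed it as serious, it stays in the SAE tables. The Week 14 admission had not happened at Parent exit, so its seriousness is decided in the extension, under the exception. Section 11.2.1.1 (asking at each visit about earlier AEs) and Section 11.2.5 (following AEs to resolution) should bring the admission to notice, but neither overrides the exception. Nothing in the documents says that a Parent AE is re-graded for seriousness when it later leads to admission.

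**Step 4. Conditions that must all hold for a loss.** (a) The condition arose after dosing. (b) An elective or planned admission was arranged before extension consent. (c) It took place after that consent. (d) No other seriousness criterion was met.

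**Step 5. Scale.** Inputs from Section 12.2: about 5 subjects per cohort and a maximum of 19 overall. Assumption: one affected subject. The change is 1/n, with exact (Clopper-Pearson) two-sided 95% limits. For 0/n the upper limit is 1 − 0.025^(1/n).

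| n | With the SAE | Without it | Change |
|---|---|---|---|
| 5 | 1/5 = 20.0% (0.5 to 71.6) | 0/5 = 0% (0 to 52.2) | 20 points |
| 19 | 1/19 = 5.3% (0.1 to 26.0) | 0/19 = 0% (0 to 17.6) | 5.3 points |

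Section 12.2 also describes about 5 subjects in each of three cohorts, or 3 × 5 = 15. On that denominator the overall change would be 1/15 = 6.7 points.

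**The case against.** The best case against the point is that the exception is narrow. It needs a planned admission, arranged before consent, for a preexisting condition. It lapses if another seriousness outcome results, including an important medical event. It affects only whether hospitalization counts as a seriousness criterion and does not delete the AE. Since preexisting is undefined, an investigator could read it as present before dosing, and the problem would not arise. All of this stands and limits the size of the point. It does not remove the point: the reading that loses the serious label is open on the text, and the consent reference is stated outright.

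Four stronger readings are tempting, and the documents do not support them.
- *Conditions arising after dosing generally drop out of the primary counts.* They do not, because Parent events are pooled into the analysis.
- *Section 11.2.1.2 is anchored to extension entry.* It does not say which study's start it means. It concerns abnormal assessments and laboratory findings that do not worsen, and the sentence before it uses the dosing baseline. It is ambiguous wording only.
- *The admission falls between the two protocols.* The Parent protocol's SAE window and post-study rules are not in the documents, so this cannot be checked.
- *The interval from dosing to consent measures the problem.* Week 12 of 24 is half the follow-up, but all four conditions in the working must hold, and consent may come before Visit 5. The interval says when the condition and the planning can occur, not how often they will.

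**Conclusion.** The point holds in a narrow form. The exception in Section 11.2.1.3 uses a reference point that comes after dosing and does not match the protocol's own definition of treatment emergence. What can be lost is the serious classification, and with it the 24-hour report, of an elective admission for a post-dose condition planned before extension consent and carried out after it, where no other seriousness criterion applies. The condition stays in the TEAE summaries.

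The table in the working assumes one affected subject. A shift of that size would follow from any single lost event in groups this small, so it shows what one case would do to the result and not how likely a case is. Severity is minor. Confidence is moderate: the conclusion takes the consent in Section 11.2.1.3 to be the extension consent, as the rest of the protocol uses the term, and it cannot take account of Parent-study rules that might catch the same admission.

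**What to change.** In Section 11.2.1.3, limit the exception to procedures planned before CLS-AX administration (Parent Visit 2, Day 1) for conditions present before that administration. Add one sentence: a Parent-study AE that later leads to hospitalization is re-assessed for seriousness during the extension. Using dosing as the single reference point also avoids a new ambiguity about procedures arranged between Parent screening and Day 1.

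As a secondary clarification, let the exemption in Section 11.2.1.2 refer to findings present at Baseline (before CLS-AX, Parent Visit 2), the reference point already used in the sentence before it.

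The cost is a few lines of text, a matching line in the CRF completion guidance, and slightly more SAE paperwork. Some admissions planned after dosing for conditions that predate it would become reportable. Since Section 12.5.2 limits the SAE summary to TEAEs, those would enter the primary count only if the condition had worsened since treatment.
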